8.1.3.2 Secondary endpoints

Safety

- Number of patients experiencing a device-related SAE (SADE) at any time during implantation and in the first 12 months (Day 0 to Day 360) following it.
- Incidence, nature, severity and seriousness of observed adverse events and adverse device events at any time during implantation and 12 months following it.

Performance

- Repeatability of the ARGOS-SC measurement
- Incidence, nature and seriousness of observed device malfunctions during implantation and in the 12 months follow-up

Utility

- User acceptance of the ARGOS-SC implantation procedure by means of evaluation of implantation procedure questionnaires (investigators)
- User acceptance of the ARGOS-SC system at the investigational site by means of evaluation of patient acceptance questionnaires (by investigators)
- User acceptance of the ARGOS-SC system at home by means of evaluation of patient acceptance questionnaires (patients)
- Daily IOP self-measurement profiles (patients)

8.1.4 Equipment to be used to assess the clinical investigation variables and arrangements for monitoring maintenance and calibration

Sites will use their own diagnostic devices. The study monitor will verify that the sites maintain and calibrate these devices on a regular basis.

Page 52 of 97

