8.3.7 Number of subjects required

This exploratory investigation will enroll 24 patients.

The overall recruitment time is expected to last a maximum of 12 months.

Page 58 of 97

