8.3.12 Performance

IOP level will be assessed at every follow-up visit in a series of 2 GAT standard measurements followed by 3 consecutive measurements with the ARGOS-SC system. From V05 (day 30) on, if available, additional 2 DCT measurements followed by 3 consecutive measurements with the ARGOS-SC system. **Optional:** At visits V06, V07 and V09, 24-hours measurements with GAT and ARGOS-SC will be done inpatient.

Patients will be given a MESOGRAPH reading device at Visit 01 in order to measure the IOP daily at home. Measurements shall be taken at least 4 times per day (morning, noon, afternoon, evening). The MESOGRAPH reading device will be connected to an external GSM module, which will transfer the measured value directly to a secure database. Investigators can log into the database in order to track the pressure levels of their patients as required. At every follow-up visit, site staff will examine the subject's hand-held reader device and download all readings recorded since the last visit. In addition, they will ask subjects non-leading questions to determine if any device deficiencies occurred since the last visit. All device deficiencies will be recorded on the device deficiency page of the CRF.

To ensure accuracy and comparability of the recorded parameters, all responsible site personnel will be thoroughly instructed on the agreed measurement methods.

To access the user acceptance of the implantation procedure and the general usability of the ARGOS-SC system, surgeons and personnel performing the ARGOS-SC system measurements will be asked to complete user acceptance questionnaires. The aim of these questionnaires is to gain more information about the level of user-acceptance of the ARGOS-SC system during implantation and during IOP measurement. The data collected with these questionnaires is only of exploratory nature and will not be included in the analysis. Results will provide the sponsor with data that could influence future device system improvements.

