8.3.13.14 Intraocular pressure (IOP) measurement

Intraocular pressure will be measured using three techniques. Goldmann Applanation Tonometry (GAT) will be performed in the clinic at every visit and if available, Pascal Dynamic Contour Tonometry (DCT) at V05 through V09. ARGOS-SC measurements will be performed in the clinic at every visit and by the patient at home between the visits. Only GAT will be used to guide any treatment decisions. The GAT and DCT must be performed by as few dedicated investigators as possible at each site to reduce potential bias.

IOP measurement in the clinic

IOP measurement will be conducted at V02 through V09 as a series of 2x GAT (in case of a difference of more than 2mmHg, a third GAT-measurement is required) followed by 3x ARGOS-SC system. When series of measurements are made, GAT must always be used first to avoid potential operator bias. For the ARGOS-SC measurements the patient has to stay in the same position as for the GAT-measurements (chin on chin rest, forehead installed). From V05 through V09 additionally (if available), a series of 2x DCT (in case of a difference of more than 2mmHg, a third DCT-measurement is required)

followed by 3x ARGOS-SC will be performed after the series of GAT and ARGOS-SC measurements. For the ARGOS-SC measurements, the patient has to stay in the same position as for the DCT-measurements (chin on chin rest, forehead installed).

Optional: At V06, V07 and V09, the patient will be hospitalized for 24-hours measurements with GAT and ARGOS-SC. IOP measurements with ARGOS-SC will be done automatically via an external antenna. IOP measurements with GAT will be done every three hours, if it is possible even at night. If night measurements are not possible every three hours at night, the last measurement should take place between 22 and 24 o'clock and the three-hours rhythm should be resumed between 5 and 7 o'clock on the next morning.

ARGOS-SC system measurement by the subject at home

Subjects will receive detailed instruction in the use of the MESOGRAPH reading device. At V02, they will receive an individual MESOGRAPH reading device, a copy of the instructions for use and the Multiline Connector to perform self-tonometry at home. Subjects will be requested to perform at least 4 IOP measurements daily with the MESOGRAPH, one each in the morning after getting up, at noon, in the afternoon and in the evening before going to bed.

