No data will be recorded manually by the subject. The MESOGRAPH reading device, which is capable of storing up to 3,000 measurements, will be connected to an external GSM module, which will transfer the measured value directly to a secure database. Investigators can log into the database in order to track the pressure levels of their patients as required.

The MESOGRAPH will also be brought to every visit, at which time site staff will assess its functionality and delete recorded IOP data from its memory.

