8.3.18 Follow-up visits (V02 to V09)

Procedures to be conducted at the early post-surgical visits include:

- Recording of Aes/SAEs/ADEs/SADEs, concomitant medications and device malfunctions
- VqoL questionnaire (V06, V07, V09)
- User acceptance questionnaire (investigator) (V09)
- User acceptance questionnaire (patient) (V09)
- Visual acuity (ETDRS)
- External eye photography (V04-V09)
- Heidelberg Engineering ANTERION[®] (optional V04-V09)
- Perimetry (V06, V07, V09)

- Anterior Segment assessments: slit-lamp biomicroscopy, AS-OCT (V04-V06), gonioscopy (V06, V07, V09)
- Posterior Segment assessments: biomicroscopy, PS-OCT (V06, V07, V09), fundus photography (V06, V07, V09)
- IOP Measurement: GAT and ARGOS-SC. Optional, if available V05 V09 Pascal DCT;
 Optional: 24-hour measurements inpatient with ARGOS-SC and GAT (V06, V07, V09)
- Instruction of subjects on the use of the MESOGRAPH and Multiline Connector
- At V02, provide the patient with a MESOGRAPH and Multiline Connector for home-use for the rest of the study. Patient should bring both devices to all subsequent visits.
- Remind subjects to promptly report any SAE that may occur at any time during the study.
- Complete the CRF and arrange the next visit.

Visit 09 is the study discharge/end of study visit. At this visit, subjects will be informed about the planned surveillance registry and asked if they wish to participate (ARGOS-SC01_Follow-up) or they will return to standard of care. At the start of the study, all patients enrolled in Switzerland will be requested to sign up for an additional follow-up of 2 years. These patients will automatically transition to the ARGOS-SC_Follow-up.

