2.9.2 Secondary endpoints

Safety:

- Number of patients experiencing a device-related SAE (SADE) at any time during implantation and in the first 12 months (day 0 to day 360) following it.
- Incidence, nature, severity and seriousness of observed adverse events (AE) and adverse device events (ADE) at any time during implantation and in the 12 months following it.

Performance:

- Repeatability of the ARGOS-SC measurement.
- Comparison of OPA measurements with the repeatability of the ARGOS-SC measurement
- Incidence, nature and seriousness of observed device malfunctions during implantation and in throughout a 12 months follow-up period.

Utility:

- User acceptance of the ARGOS-SC implantation procedure by means of evaluation of implantation procedure questionnaires (surgeon)
- User acceptance of the ARGOS-SC system at the investigational site by means of evaluation of patient acceptance questionnaires (by investigators)
- User acceptance of the ARGOS-SC system at home by means of evaluation of patient acceptance questionnaires (patients)

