4.6.3 Further endpoints

- User acceptance of the ARGOS-SC implantation procedure by means of evaluation of implantation procedure questionnaires (investigators) at V01 (statistical parameters)
- User acceptance of the ARGOS-SC system at the investigational site by means of evaluation of patient acceptance questionnaires (by investigators) at V09 (statistical parameters)
- User acceptance of the ARGOS-SC system at home by means of evaluation of patient acceptance questionnaires (patients) at V09 (statistical parameters)
- Repeatability of the ARGOS-SC measurement (statistical parameters)
- Concomitant glaucoma medication is shown separately as follows:
 - Previous glaucoma medication (stopped before implantation): in total (N,%) and stratified by ingredients (N, %) (Mock-up Table 3a)
 - Concomitant glaucoma medication (medication given during V01 V09): in total (N, %) and stratified by ingredients (N, %) (Mock-up Table 3b)

- Other concomitant medication is shown separately as follows:
 - Previous medication (stopped before implantation): in total (N, %) and stratified by ingredients (N, %)
 - Concomitant medication (medication given during V01 V09): in total (N,
 %) and stratified by ingredients (N, %)
- NEI VFQ-25 questionnaire:
 - 25 items in course of study (statistical parameters)
 - 12 sub-scales in course of study (statistical parameters)
 - Changes from baseline of the 12 sub-scales (statistical parameters)

The changes from baseline of the 12 sub-scales will be analysed by means of paired t-Test (in case of normal distribution) or the Wilcoxon sign rank test (in case of non-normal distribution). The Mixed Model repeated measurement (MMRM) analysis of covariance for repeated measures in mixed models (V06, V07, V09 vs. Screening) will be used in addition.

 Daily IOP self-measurement profiles (patients) will not be included into the evaluation.

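### The SAP leaves out, without a reason, a secondary endpoint the protocol lists: the daily pressure profiles patients record at home

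*SAP*

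**What the plan says.** **Protocol.** Section 8.1.3.2 lists four Utility items among the secondary endpoints, and the last is "Daily IOP self-measurement profiles (patients"). The synopsis lists the same four. Section 8.3.12 sets the frequency: "Measurements shall be taken at least 4 times per day (morning, noon, afternoon, evening"). Section 8.3.13.14 repeats it ("Subjects will be requested to perform at least 4 IOP measurements daily with the MESOGRAPH") and says the reader is linked to a GSM module "which will transfer the measured value directly to a secure database". At V02, according to section 8.3.18, sites are to "provide the patient with a MESOGRAPH and Multiline Connector for home-use for the rest of the study".

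**SAP.** Section 2.9.2 carries over the three questionnaire items and stops at "User acceptance of the ARGOS-SC system at home by means of evaluation of patient acceptance questionnaires (patients"). The fourth item is absent. Section 4.6.3 closes its list with "Daily IOP self-measurement profiles (patients) will not be included into the" evaluation, and gives no explanation. The flow chart in section 2.10 and its footnote nevertheless keep home self-measurement at the same four-a-day minimum.

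**The restriction both documents share.** Protocol 9.11.2 and SAP 3.7 say that home readings, taken at differing times and in differing conditions, are not expected to be comparable with clinic readings. They are therefore left out of the per-protocol agreement analysis.

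**The concern.** Following the SAP as written leaves an endpoint named in the protocol without any analysis, and neither document says why. The endpoint is not peripheral. Frequent self-measurement at home is the benefit on which the protocol rests the case for the implant: section 3.3 on advantages, 6.1 on anticipated benefits and 6.7 on the risk/benefit balance. Patients are asked to measure for a year, and the data are stored electronically.

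Without the profiles, the main evidence on home use is a single patient acceptance questionnaire at V09. It records opinion at about day 360. It cannot show whether patients kept up four readings a day through the year, or what their pressures looked like across the day.

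The change may also go unexplained in the final report. Protocol 9.8 requires departures from the SAP to be listed and clarified there. It does not clearly cover a departure from the protocol that is written into the SAP itself.

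**Working it through.** The documents state no figure for the volume of home data, so there is nothing to reproduce. The check is a comparison of the passages, followed by a simple count.

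**1. Endpoint lists, Utility**

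| Item | Protocol 8.1.3.2 and synopsis | SAP 2.9.2 | SAP 4.6.3 |
|---|---|---|---|
| Implantation procedure questionnaire | listed | listed | summarised |
| Investigator acceptance questionnaire | listed | listed | summarised |
| Patient acceptance questionnaire (home) | listed | listed | summarised |
| Daily home pressure profiles | listed | absent | excluded, no reason |

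**2. Does the protocol's own restriction explain the gap?** Section 9.11.2 limits one use of home readings, their comparison with clinic tonometry in the per-protocol set. Describing a patient's own home readings over time needs no such comparison. The protocol contains both the restriction and the endpoint, so it treats them as compatible.

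**3. Does anything else in the two documents restore the analysis?** No. The study variables in SAP 2.8 do not include home readings. The 24-hour series at V06, V07 and V09 is an inpatient measurement.

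**4. Volume of home data**

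Inputs:
- Patients: 24 (Protocol 8.3.7, "This exploratory investigation will enroll 24 patients").
- Readings per day: at least 4 (Protocol 8.3.12 and 8.3.13.14).
- Days: to V09 at day 360. The start is stated in two ways. Protocol 8.3.13.14 and 8.3.18 issue the reader at V02 (day 1), while 8.3.12 and Table 1 point to V01 (day 0).

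Formula: readings = patients × readings per day × days.

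- From day 1: 360 − 1 = 359 days. 4 × 359 = 1,436 per patient, and 24 × 1,436 = 34,464 in total.
- From day 0: 360 days. 4 × 360 = 1,440 per patient, and 24 × 1,440 = 34,560 in total.

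Both totals assume full adherence at the four-a-day minimum and no dropout. If patients took half the requested readings (an assumption for illustration), the range would be 34,464 / 2 = 17,232 to 34,560 / 2 = 17,280.

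For scale, the scheduled clinic visit-level pairs of GAT and ARGOS-SC number at most 24 × 8 = 192.

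**5. What is not touched.** The primary endpoint uses clinic measurements. The pass/fail criteria in Protocol 9.5 use serious adverse device effects and the agreement between GAT and ARGOS-SC. Neither depends on home readings.

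**The case against.** The strongest defence has several parts.

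- **The exclusion is declared.** SAP 4.6.3 says plainly that the profiles are left out. A reader might infer selective non-reporting, especially in an open-label trial with planned evaluations at V06 and V07. The documents do not support that: nothing shows that home data were looked at before the decision. Nor do they show that the profiles will never be reported, since the SAP governs its own evaluation and a listing or separate report remains possible. This part stands.
- **Utility is still assessed.** The three questionnaire endpoints remain, and SAP 4.6.2 tabulates deficiencies of the reader. A reader might infer that the utility question goes unanswered, but only one component is lost: patterns of use and pressure at home. This also stands.
- **No analysis was ever defined.** Protocol section 9 gives no summary measure for the profiles, so the SAP drops a named endpoint and not a specified analysis. That is true, but defining the analysis of a named endpoint is the SAP's job.
- **An amendment might have removed it.** SAP 3.2 says the SAP incorporates all amendments, and SAP 4.1.5 cites an Addendum I whose text is not supplied. The citation concerns the interim analysis only. This is a caveat and does not rebut the point.
- **The count measures volume, not harm.** This stands. Nor are the readings wholly unused, since investigators can view them during the trial. What is missing is their analysis under the SAP.

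None of this supplies a reason for the exclusion.

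**Conclusion.** The inconsistency is confirmed. A secondary Utility endpoint in the protocol is omitted from SAP 2.9.2 and excluded by SAP 4.6.3 without a reason, while collection of the data continues. Protocol 9.11.2 does not cover the exclusion.

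The effect is moderate. A descriptive endpoint on the device's central claimed benefit is lost, and about 34,500 readings would go unanalysed under this SAP if 24 patients measured four times daily without dropout. The number would be lower with missed readings or withdrawals and higher if patients measured more often.

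A reader might also take this for the loss of a registered endpoint. No registry record is available, and Protocol 13.3 does not say which endpoints would be registered, so the supportable description is an endpoint specified in the protocol. The conclusion also assumes that the unseen addendum does not change this endpoint.

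**What to change.** Restore the endpoint in SAP 2.9.2 and add a descriptive analysis in SAP 4.6.3. A workable set, per patient, would be:
- the share of days with at least four readings;
- the daily mean, minimum, maximum and range;
- the profile by time of day.

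These summaries are a suggestion, since the protocol defines none. Include failed readings only if the database stores them; the documents mention transfer of measured values only. State the start of the home period, because the protocol gives both V01 and V02. Keep home readings out of the agreement analysis, as Protocol 9.11.2 and SAP 3.7 already provide.

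If the sponsor does intend to drop the endpoint, amend the protocol to remove it and state the reason there and in the SAP.

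The cost of restoring it is some extraction and programming. Protocol 10.4 names the measurement database separately from the clinical data management database, so the readings may have to be extracted and linked to the clinical data. No new data collection and no change in sample size are needed.

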4.7 Other topics of data analysis: Coding

- Reconditioning / coding of adverse events, diagnoses, and concomitant diseases
 will be conducted by *Implandata Ophthalmic Products*
- Coding of concomitant medication by ingredients will be conducted by *Implandata* Ophthalmic Products

5 Mock-up tables and figures

Table 1(dummy data)

able 1(dummy data)						
Demographic data						
Gender	N	50				
	male	20 (40.0%)				
	female	30 (60.0%)				
Age [years]	N					
	Mean					
	Mean [95% CI]					
	Standard dev.					
	25Percentile					
	Median					
	75Percentile					
	Minimum					
	Maximum					

Table 2

IOP measurements: GAT and ARGOS-SC										
		Visit V02	Visit V03	Visit V04	Visit V05	Visit V06				
GAT	N	22	22	21	22	17				
	Mean	7.36	9.82	12.81	13.05	12.24				
	Mean [95% CI]	5.03 9.70	7.19 12.45	10.45 15.17	10.93 15.16	10.13 14.34				
	SD	5.26	5.93	5.18	4.78	4.10				
	25Percentile	3.00	6.00	7.00	10.00	11.00				
	Median	5.50	8.50	13.00	13.00	12.00				
	75Percentile	9.00	12.00	17.00	17.00	14.00				
	Minimum	2.0	2.0	6.0	4.0	4.0				
	Maximum	24.0	27.0	22.0	24.0	19.0				
ARGOS-SC	N	21	21	20	22	17				
	Mean	8.24	10.52	15.05	14.95	12.65				
	Mean [95% CI]	5.77 10.7	8.23 12.82	11.53 18.57	12.10 17.81	9.25 16.04				
	SD	5.42	5.05	7.51	6.45	6.60				
	25Percentile	5.00	7.00	8.50	11.00	9.00				
	Median	7.00	9.00	15.50	14.50	12.00				
	75Percentile	11.00	14.00	20.00	18.00	14.00				
	Minimum	2.0	3.0	4.0	4.0	5.0				
	Maximum	24.0	22.0	31.0	29.0	33.0				
Difference	N	21	21	20	22	17				
	Mean	0.81	0.71	2.20	1.91	0.41				
	Mean [95% CI]	-0.17 1.79	-0.86 2.29	0.31 4.09	0.41 3.41	-1.84 2.67				
	SD	2.16	3.47	4.05	3.38	4.39				
	25Percentile	0.00	-2.00	-0.50	0.00	-2.00				
	Median	1.00	1.00	2.50	2.00	0.00				
	75Percentile	2.00	4.00	3.50	5.00	1.00				
	Minimum	-2.0	-7.0	-5.0	-4.0	-4.0				
	Maximum	6.0	6.0	13.0	7.0	15.0				

IOP measur	IOP measurements: GAT and ARGOS-SC								
		Visit V02	Visit V03	Visit V04	Visit V05	Visit V06			
Absolute	N	21	21	20	22	17			
difference	≤ 5 mmHg	20 (95.2%)	18 (85.7%)	18 (90.0%)	17 (77.3%)	16 (94.1%)			
	> 5 mmHg	1 (4.8%)	3 (14.3%)	2 (10.0%)	5 (22.7%)	1 (5.9%)			
	rccc	0.91	0.80	0.76	0.78	0.68			

[figure not shown]

Table 3a

Previous medication due to glaucoma					
Drug / ingredients					
Brinzolamides					
Total	N (%)				

Table 3b

Concomitant medication due to glaucoma								
Drug / ingredients Begin + - End								
Brimonidine	10	15	3	22				
Brinzolamides								
Total								

Begin: administration at V01
+ started during the study
